11.1.3.1 Evaluation of Target Lesions

Complete Response (CR): Disappearance of all target lesions. Any pathological lymph nodes (whether target or non-target) must have reduction in short axis to <10 mm.

Partial Response (PR): At least a 30% decrease in the sum of the diameters of target lesions, taking as reference the baseline sum diameters.

Progressive Disease (PD): At least a 20% increase in the sum of the diameters of target lesions, taking as reference the smallest sum on study (this includes the baseline sum if that is the smallest on study). In addition to the relative increase of 20%, the sum must also demonstrate an absolute increase of at least 5 mm. (Note:

the appearance of one or more new lesions is also considered progressions).

Stable Disease (SD): Neither sufficient shrinkage to qualify for PR nor sufficient increase to qualify for PD, taking as reference the smallest sum diameters while on study.

11.1.3.2 Evaluation of Non-Target Lesions

Complete Response (CR): Disappearance of all non-target lesions and normalization of tumor marker level. All lymph nodes must be non-pathological in size (<10 mm short axis).

Note: If tumor markers are initially above the upper normal limit, they must normalize for a patient to be considered in complete clinical response.

Non-CR/Non-PD: Persistence of one or more non-target lesion(s) and/or maintenance of tumor marker level above the normal limits.

Progressive Disease (PD): Appearance of one or more new lesions and/or *unequivocal progression* of existing non-target lesions. *Unequivocal progression* should not normally trump target lesion status. It must be representative of overall disease status change, not a single lesion increase.

Although a clear progression of “non-target” lesions only is exceptional, the opinion of the treating physician should prevail in such circumstances, and the progression status should be confirmed at a later time by the review panel (or Principal Investigator).

11.1.3.3 Evaluation of New Lesions

The finding of a new lesion should be unequivocal (i.e. not due to difference in scanning technique, imaging modality, or findings thought to represent something other than tumor (for example, some ‘new’ bone lesions may be simply healing or flare of pre-existing lesions). However, a lesion identified on a follow-up scan in an anatomical location that was not scanned at baseline is considered new and will indicate PD. If a new lesion is equivocal (because of small size etc.), follow-up evaluation will clarify if it truly represents new disease and if PD is confirmed, progression should be declared using the date of the initial scan on which the lesion was discovered.

11.1.3.4 Evaluation of Best Overall Response

The best overall response is the best response recorded from the start of the treatment until disease progression/recurrence (taking as reference for progressive disease the smallest measurements recorded since the treatment started). The patient's best response assignment will depend on the achievement of both measurement and confirmation criteria.

Table 17: For Participants with Measurable Disease (i.e., Target Disease)

Target Lesions	Non-Target Lesions	New Lesions	Overall Response	Best Overall Response when Confirmation is Required*
CR	CR	No	CR	≥ 4 wks Confirmation**
CR	Non-CR/Non-PD	No	PR	≥ 4 wks Confirmation**
CR	Not evaluated	No	PR	
PR	Non-CR/Non-PD/not evaluated	No	PR	Documented at least once ≥ 4 wks from baseline**
SD	Non-CR/Non-PD/not evaluated	No	SD	
PD	Any	Yes or No	PD	no prior SD, PR or CR
Any	PD***	Yes or No	PD	
Any	Any	Yes	PD	

* See RECIST 1.1 manuscript for further details on what is evidence of a new lesion.

** Only for non-randomized trials with response as primary endpoint.

*** In exceptional circumstances, unequivocal progression in non-target lesions may be accepted as disease progression.

Note: Participants with a global deterioration of health status requiring discontinuation of treatment without objective evidence of disease progression at that time should be reported as “*symptomatic deterioration*.” Every effort should be made to document the objective progression even after discontinuation of treatment.

Table 18: For Participants with Non-Measurable Disease (i.e., Non-Target Disease)

Non-Target Lesions	New Lesions	Overall Response
CR	No	CR
Non-CR/non-PD	No	Non-CR/non-PD*
Not all evaluated	No	not evaluated
Unequivocal PD	Yes or No	PD
Any	Yes	PD

* ‘Non-CR/non-PD’ is preferred over ‘stable disease’ for non-target disease since SD is increasingly used as an endpoint for assessment of efficacy in some trials so to assign this category when no lesions can be measured is not advised

11.1.4 Duration of Response

Duration of overall response: The duration of overall response is measured from the time measurement criteria are met for CR or PR (whichever is first recorded) until the first date that recurrent or progressive disease is objectively documented (taking as reference

for progressive disease the smallest measurements recorded since the treatment started, or death due to any cause. Participants without events reported are censored at the last disease evaluation).

Duration of overall complete response: The duration of overall CR is measured from the time measurement criteria are first met for CR until the first date that progressive disease is objectively documented, or death due to any cause. Participants without events reported are censored at the last disease evaluation.

Duration of stable disease: Stable disease is measured from the start of the treatment until the criteria for progression are met, taking as reference the smallest measurements recorded since the treatment started, including the baseline measurements.

11.1.5 Response Review

Imaging will be reviewed at the Tumor Imaging Metrics Core (TIMC).

12. DATA REPORTING / REGULATORY REQUIREMENTS

Adverse event lists, guidelines, and instructions for AE reporting can be found in Section 7.0 (Adverse Events: List and Reporting Requirements).

12.1 Data Reporting

12.1.1 Method

The Office of Data Quality (ODQ) will collect, manage, and perform quality checks on the data for this study.

12.1.2 Responsibility for Data Submission

Investigative sites within DF/HCC or DF/PCC are responsible for submitting data and/or data forms to the Office of Data Quality in accordance with DF/HCC SOPs.

12.2 Data Safety Monitoring

The DF/HCC Data and Safety Monitoring Committee (DSMC) will review and monitor toxicity and accrual data from this study. The committee is composed of clinical specialists with experience in oncology and who have no direct relationship with the study. Information that raises any questions about participant safety will be addressed with the Overall PI and study team.

The DSMC will review each protocol up to four times a year or more often if required to review toxicity and accrual data. Information to be provided to the committee may include: up-to-date participant accrual; current dose level information; DLT information; all grade 2 or higher

unexpected adverse events that have been reported; summary of all deaths occurring with 30 days of intervention for Phase I or II protocols; for gene therapy protocols, summary of all deaths while being treated and during active follow-up; any response information; audit results, and a summary provided by the study team. Other information (e.g. scans, laboratory values) will be provided upon request.

13. STATISTICAL CONSIDERATIONS

13.1 Study Design/Endpoints

This is an open label phase II study evaluating potential immunologic biomarkers of response and resistance to first-line ipilimumab and nivolumab therapy in non-small cell lung cancer (NSCLC). The primary objective of the trial is to determine whether combination therapy with ipilimumab and nivolumab confers a promising best overall objective response rate per RECIST 1.1 in this patient population. Secondary objectives include estimation of progression-free survival, overall survival, and toxicity.

13.1.1 Study Endpoints

Best objective response will be evaluated via RECIST1.1 criteria. Progression-free survival (PFS) is defined as the time from registration to documented disease progression or death from any cause, whichever occurs first. Patients who have not experienced an event of interest by the time of analysis will be censored at the date they are last known to be alive and progression-free. Overall survival is defined as the time from registration to death from any cause, and patients who are thought to be alive at the time of final analysis will be censored at the last date of contact. Duration of response is defined as the time from tumor response to documented disease progression or death from any cause, whichever occurs first. Patients who have not experienced an event of interest by the time of analysis will be censored at the date they are last known to be alive and progression-free. Toxicity will be determined using the CTCAE version 4.0 criteria.

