4. REGISTRATION PROCEDURES

4.1 General Guidelines for DF/HCC Institutions

Institutions will register eligible participants in the Clinical Trials Management System (CTMS) OnCore. Registrations must occur prior to the initiation of protocol therapy. Any participant not registered to the protocol before protocol therapy begins will be considered ineligible and registration will be denied.

An investigator will confirm eligibility criteria and a member of the study team will complete the protocol-specific eligibility checklist.

Following registration, participants may begin protocol therapy. Issues that would cause treatment delays should be discussed with the Overall Principal Investigator (PI). If a participant does not receive protocol therapy following registration, the participant's registration on the study must be canceled. Registration cancellations must be made in OnCore as soon as possible.

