10. STUDY CALENDAR

Baseline evaluations are to be conducted within 14 days prior to the start of protocol therapy. The informed consent and baseline tumor imaging may be obtained up to 28 days prior to the start of protocol therapy. In the event that the participant's condition is deteriorating, laboratory evaluations should be repeated within 48 hours prior to initiation of the next cycle of therapy.

Assessments must be performed prior to administration of any study agent.

Table 16: Study Calendar									
	Pre-Study	Cycle 1 Day 1	Cycle 1 Day 15 ^A	Cycle 1 Day 29 ^A	Cycle 2+ Day 1 ^B	Cycle 2+ Day 15 ^A	Cycle 2+ Day 29 ^A	Off Treatment ^C	Long-term Follow Up ^D
Informed consent	X								
Demographics	X								
Medical history	X								
Physical exam	X	X	X	X	X	X	X	X	
Vital signs ^E	X	X	X	X	X	X	X	X	
Height	X								
Weight	X	X	X	X	X	X	X	X	
ECOG Performance Status	X	X			X			X	
CBC w/diff, plts	X	X	X	X	X	X	X	X	
Serum chemistry ^F	X	X	X	X	X	X	X	X	
TSH	X				X				
ACTH	X				X				
Amylase and Lipase	X				X				
Adverse event evaluation	X	X-----X						X	
Radiologic evaluation	X	CT or MRI imaging of any disease-involved site. Imaging evaluations to be obtained at baseline and then every 6 weeks × 6 cycles (-3 day/+7 day scheduling window). Brain MRI is required for all patients at baseline, and every 12 weeks on study for patients with CNS disease. At the completion of 6 cycles of therapy, at the treating investigator's discretion, imaging may be moved to every 12 weeks (-14 day/+7 day scheduling window). Participants who discontinue treatment prior to documented disease progression should continue to be followed for radiologic response every 12 weeks until documented disease progression or death.						X	X
Serum β-HCG ^G	X								
Nivolumab Infusion ^H		X	X	X	X	X	X		
Ipilimumab Infusion ^H		X			X				

Table 16: Study Calendar									
	Pre-Study	Cycle 1 Day 1	Cycle 1 Day 15 ^A	Cycle 1 Day 29 ^A	Cycle 2+ Day 1 ^B	Cycle 2+ Day 15 ^A	Cycle 2+ Day 29 ^A	Off Treatment ^C	Long-term Follow Up ^D
Fresh Tumor Tissue Biopsy ^I	X			X ^I				X	
Archival Tumor Tissue Collection	X								
Plasma Collection	X				X			X	
PBMC Collection ^J	X				X			X	
Telephone or Care Provider Contact									X

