13.1.3 Statistical Analysis Plan

The primary and some secondary analyses will include all eligible and treated patients. Exceptions to this include: analysis of toxicity data, which will include all patients who received study drug regardless of eligibility.

Time-to-event data, such as PFS and OS, will be estimated using the Kaplan-Meier method, and Cox proportional hazards models will be used to estimate hazard ratios. Comparisons of groups will be made using the logrank test and Cox modeling.

Categorical data, such as response rates (CR+PR) and toxicity, will be compared using Fisher's exact tests with a one-sided type I error rate of 10%; multivariable logistic regression modeling will be used to adjust for the effect of any covariates that are associated with these categorical outcomes. Though none are currently planned, any continuous outcomes will be analyzed using Wilcoxon rank sum test, and multivariable linear regression models may be used to adjust for multiple associations with outcome.

Modeling procedures will implement backward selection; variables significant at the 0.10 level in the univariate setting will be chosen for inclusion in an initial full model, and at each step the least significant variable will be removed from the model. Only those covariates with $p < 0.05$ will remain in any final models, unless there are factors identified by the study team as crucial to model interpretation.

Point estimates of all endpoints will be accompanied by the corresponding two-sided 80% confidence intervals. The method of Atkinson and Brown will be used for the estimation of the confidence interval for response.

In the event that there are missing data, no imputation of the missing data will be conducted. We will assume that data are missing at random and will conduct all analyses as originally planned because we do not anticipate an excess of missing data.

Subset analyses of all variables, including correlatives, are considered to be exploratory in nature.

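### PFS and OS are timed from registration, but untreated registrations are cancelled, so any wait before the first dose counts as survival time

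*Combined protocol and SAP*

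**What the plan says.** Section 13.1.1 starts both time-to-event endpoints at registration: "Progression-free survival (PFS) is defined as the time from registration to documented disease progression or death from any cause, whichever occurs first", and "Overall survival is defined as the time from registration to death from any cause".

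Section 4.1 fixes the order of events: "Registrations must occur prior to the initiation of protocol therapy". It then removes those who never start: "If a participant does not receive protocol therapy following registration, the participant's registration on the study must be canceled". It foresees treatment delays after registration and sets no limit on the interval from registration to first dose.

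On the analysis population, section 13.1.3 says: "The primary and some secondary analyses will include all eligible and treated patients". PFS and OS are not named. The one exception listed is toxicity, and that set also requires study drug.

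Two windows in section 10 bear on the gap. First: "Baseline evaluations are to be conducted within 14 days prior to the start of protocol therapy". Second, consent and baseline imaging may be up to 28 days before the start of therapy.

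Other measures start at treatment. In section 11.1.4: "Stable disease is measured from the start of the treatment until the criteria for progression are met". Section 11.1.3.4 likewise counts best overall response from the start of treatment.

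**The concern.** The time origin and the population do not match. The clock starts at registration, but a patient stays in the data only by reaching the first dose. A death between the two leads to a cancelled registration and drops out. For everyone who remains, the same interval is counted as time survived. This is guaranteed survival time, and enlarging the sample does not remove it.

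The loss can also be selective. Section 5.2.1 requires laboratory tests older than 96 hours to be repeated on Cycle 1 Day 1 and to meet eligibility again, subject to exceptions agreed with the principal investigator. A patient who deteriorates after registration can therefore go undosed and be cancelled.

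For PFS the guarantee is practical, not absolute. No scan is scheduled between baseline and week 6 (sections 10 and 11.1), so progression before the first dose would seldom be documented. At stake are two named secondary endpoints (sections 1.3 and 13.1), each of which could be reported as somewhat longer than it is from first dose.

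**Working it through.** **1. The plan's own design figures.** Sections 13.1.2 and 13.1.3 state no figure for PFS or OS. The main design calculation is the two-stage rule for response: continue with at least 15 of 43, succeed with at least 29 of 80, with response rates of 30% and 44%.

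- Early stopping under the null = P(X ≤ 14 | n = 43, p = 0.30) = 0.708 (stated 0.71).
- Success probability = sum over x ≥ 15 of P(X₁ = x) × P(X₂ ≥ 29 − x | n = 37). This is 0.1092 at p = 0.30 (stated 0.109) and 0.884 at p = 0.44 (stated 88%).

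All three reproduce, and none depends on when the PFS or OS clock starts.

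**2. Inputs for the size of the bias.**

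- Arm Q in Table 2 (section 2.4.3): 12-month PFS 35% (95% CI 20 to 50) and median OS 18.1 months. These serve only as a realistic scale.
- Gap g: not stated. Assumed range 0 to 14 days, from the baseline-evaluation window in section 10, because eligibility confirmed at registration depends on those evaluations. 28 days, the consent and imaging window, is the outer bound.
- Constant hazard, the same gap g for every patient, and 30.4375 days per month.

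**3. Formulas.** If no event can be counted in the gap, then:

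- h = −ln(0.35)/12 = 0.0875 per month, and median PFS from first dose = ln 2/h = 7.92 months.
- Reported 12-month PFS = exp(−h(12 − g)).
- Reported median = median from first dose + g.

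For 14 days, g = 14/30.4375 = 0.46 months, and exp(−0.0875 × 11.54) = 0.364.

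| Gap (days) | 12-month PFS | Median PFS (months) | Median OS (months) |
|---|---|---|---|
| 0 | 35.0% | 7.92 | 18.1 |
| 3 | 35.3% | 8.02 | 18.2 |
| 7 | 35.7% | 8.15 | 18.3 |
| 14 | 36.4% | 8.38 | 18.6 |
| 28 | 37.9% | 8.84 | 19.0 |

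A 14-day gap adds 5.8% to median PFS and 2.5% to median OS. A 28-day gap adds 11.6% and 5.1%.

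**4. Sensitivity to the anchor.** With 12-month PFS at the ends of the arm Q interval, a 14-day gap moves 20% to 21.3% and 50% to 51.4%. A 28-day gap moves them to 22.6% and 52.7%. The shift in points hardly changes.

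**5. Deaths lost.** With h = ln 2/18.1, expected deaths in the gap per 80 registered = 80 × (1 − exp(−hg)). This is 0.7 at 7 days, 1.4 at 14 days and 2.8 at 28 days.

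**6. Against sampling error.** Section 13.1.3 specifies two-sided 80% intervals. For a 35% rate with n = 80 and no censoring, the half-width is 1.2816 × √(0.35 × 0.65/80) = 0.068, or 6.8 points. The shift is 1.4 points at 14 days and 2.9 points at 28 days.

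**The case against.** The strongest reply is that the effect is small and may be absent. Section 4.1 requires only that registration come before therapy, so same-day dosing is allowed and the gap can be zero. Registration rests on eligibility evaluations that should fall within 14 days of starting therapy. The 28-day window covers consent and imaging, not registration. Within 0 to 14 days the shift is well inside the sampling error. All of this stands, and it limits severity.

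A second reply is that section 13.1.1 defines the endpoints clearly and in advance, and that PFS and OS need not share an origin with best response or duration of stable disease. That also stands: the differing origins are not a contradiction in themselves. The problem is the combination of a registration origin with a set that excludes the untreated.

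A reader might infer four stronger things that the documents do not support:

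- *That every patient carries an event-free interval.* Same-day dosing gives none. A patient who progresses before dosing and is still treated stays in the analysis.
- *That the gap differs by tissue route.* Sections 3.1.8 and 9.1 let those without sufficient archival tissue enrol after the fresh biopsy, but section 9.2 makes that biopsy a condition of enrolment for all.
- *That the results will be read against Table 2.* No such comparison is planned, and Table 2 does not give its own time origin.
- *That the plan restricts PFS and OS to treated patients in so many words.* It does not name their population. The restriction follows from the cancellation rule.

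**Conclusion.** The point holds as a low-severity, one-directional bias. Any treated patient dosed after the day of registration contributes guaranteed survival time and, in practice, nearly guaranteed progression-free time. Under the stated assumptions (constant hazard, arm Q values, a common gap of 0 to 14 days), the overstatement is 0 to 1.4 points on 12-month PFS and 0 to 0.46 months on either median. The 28-day figures, 2.9 points and 0.92 months, are a worst case and should not be taken as typical. The actual gap cannot be known from the documents.

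The response rate, the two-stage rule and duration of response are unaffected. Hazard ratios between biomarker groups would change little if the gaps are similar across groups.

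**What to change.** - In section 13.1.1, define PFS and OS from the date of first dose (Cycle 1 Day 1).
- In section 13.1.3, state that PFS and OS are analysed in the eligible-and-treated set.
- Report the distribution of the registration-to-dose interval, and the number of cancelled registrations with reasons.
- State how progression documented before the first dose would be handled, since it would precede the new time zero.

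Keeping registration as the origin and retaining all eligible registered patients, treated or not, would also make origin and population agree. It would mean following participants whose registration section 4.1 now cancels, so it is the larger change.

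The recommended version costs a few words of text and no added patient procedures. Its downside is that the reported PFS and OS become slightly less favourable.

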13.1.2 Sample Size Considerations

The primary comparison will include all eligible and treated patients, of whom 80 will be accrued. Whereas traditional chemotherapy confers a response rate (CR + PR) of roughly 30%, the goal of this trial is to target a response rate of 44%, which will be taken as evidence of activity of combination therapy with ipilimumab and nivolumab. We will employ a Simon two stage design for this trial. In the first stage, a total of 43 eligible and treated patients will be enrolled. Accrual will proceed to the second stage if at least 15 patients achieve a CR or PR among those first 43 patients. In the second stage, an additional 37 patients will be enrolled. If at least 29 responses are observed among all 80 patients enrolled, then the combination of ipilimumab and nivolumab will be deemed worthy of additional study. This trial has 88% power against the null hypothesis while testing at the one-sided level of 0.109, and the probability that the study stops early under the null is 0.71.

We note that per RECIST 1.1, these responses must be confirmed with a second scan after the

initial response is determined. We also note that patients who are deemed unevaluable for response will not be replaced, and will be included as non-responders in the assessment of the best objective response rate.

